9.3 Variables

9.3.1 Baseline characteristics

Baseline period:

365 days prior to index date for hospital diagnoses and prescriptions and four quarters prior to the index quarter for ambulatory diagnosis. This period will be used to determine whether patients have an NVAF diagnosis, to verify that patients are new users and to assess baseline demographic and clinical characteristics of the patients included in the study population.

The following demographics will be reported for each cohort:

- Gender
- Age
- Age group
 - 18-65, 65-74, ≥ 75

The following clinical characteristics will be reported for each cohort:

- 4-quarter Charlson comorbidity index (CCI)
- CKD, which is important as risk of adverse events among patients receiving NOACs tends to differ according to renal function)
- CHADS₂ score, including Congestive heart failure, hypertension, age, diabetes, stroke
- CHA₂DS₂-Vasc score
- HASBLED score, as measurable without lab values
- Prior non-CNS systemic embolism
- Prior oral anticoagulant use (expected to be 0 with 180-day covariate look back)
- Other relevant co-morbidities:
 - Congestive heart failure
 - DVT
 - Essential hypertension
 - Diabetes mellitus
 - Pulmonary embolism
 - Unstable angina
 - Hyperthyroidism
 - Functional dyspepsia
 - Renal failure

- Other cardiovascular drugs:
 - Antiarrhythmics
 - Beta blockers
 - ACE inhibitors
 - ARBs
 - Calcium channel blockers
 - Diuretics
 - Anti-platelet drug classes
 - NSAIDS

Stroke risk score CHADS₂ and CHA₂DS₂-VASc

Stroke risk scores in the individual pre-index period of 4 quarters before the index quarter with defined risk factors and corresponding ICD-10-GM codes including heart failure, hypertension, age groups, diabetes mellitus, stroke/TIA/embolism, vascular disease and gender (listed in Annex 2, Table 7).

To include Health Care Proxies

- Number of hospitalizations in the baseline period
- Number of unique medications in the baseline period

Comorbidities

Presence of relevant comorbidities e.g. hemorrhagic diathesis due to anticoagulants and antibodies, coagulopathy, hyperthyroidism, etc. (see Annex 2, Table 6) in the inpatient sector (main and secondary diagnoses) or in the outpatient sector (verified diagnoses and in addition “condition after diagnoses” for stroke, bleedings and MI) in the patient’s medical history in the individual pre-index period of 4 quarters before the index quarter will be assessed.

Co-medications

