9.7.1.2 Primary and secondary objectives

The incidence rate and corresponding confidence intervals of the primary and secondary endpoints will be estimated as the number of events per 100 person years (% per year). Cox proportional hazard regression will be used to estimate unadjusted and adjusted hazard ratios (multivariate adjusted as well as 1:1 propensity matched). For all models, hazard ratios (HRs), 95% confidence intervals (CIs) and all other regression coefficients will be reported.

Kaplan-Meier curves will be generated to evaluate the time-to-first event associated with the initial treatment.

Rivaroxaban will be compared to Phenprocoumon. Hence, Phenprocoumon will be the reference category in the analysis. A subset of the variables depicted in Table 2 which were selected on an empirical basis, will be included as covariates in the Cox proportional hazards model.

Propensity Score Matching

In this study, we will additionally use propensity score matching. The propensity score will be calculated as the predicted probability of exposure (i.e. probably of receiving Rivaroxaban), given all that is known about a patient (i.e. patient characteristics and covariates).

The probability itself will be derived from a multivariate logistic regression using the parameters thought to act as confounding variables. The propensity score act as a “balancing score” in that all factors that contribute to the score are expected to be independent between treatment groups if the patient population is matched on propensity score and a stratified table of patient characteristics is examined. That is, after propensity score matching all other factors included in the score are expected to be balanced between the two treatment groups. This will minimize confounding by observed baseline covariates by removing any potential relationship between cofounders and exposure group.

In this study, we will estimate propensity scores from all measured factors noted above. These factors will be entered into a logistic regression model, with the factors as the independent variables (with no further variable selection) and the treatment as the dependent variable. From the resulting model, we will predict probability of treatment for each patient; this probability of treatment will be each patient’s estimated propensity score.

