Hemorrhagic diathesis due to anticoagulants and antibodies Coagulopathy, not specified Hyperthyroidism Diabetes mellitus Hyperlipidemia Cerebral transitory ischemia and related problems Essential hypertension Angina pectoris Myocardial infarction Other acute ischemic heart disease Chronic ischemic heart disease Pulmonary embolisms Heart failure Intracerebral hemorrhage Other non-traumatic intracranial bleeding Cerebral infarction Stroke, not referred to as bleeding or infarction Hemorrhage or intracranial bleeding or cerebral infarction or stroke Peripheral vascular disease, not specified Deep thrombosis on leg and pelvic veins Functional dyspepsia Hepatic insufficiency Renal insufficiency Chronic renal disease, stage 1 Chronic renal disease, stage 2 Chronic renal disease, stage 3 Chronic renal disease, stage 4 Chronic renal disease, stage 5 Cancer Gastrointestinal bleeding*		

Table 22 – Co-mediations before matching

	Rivaroxaban patients (n, %)	VKA patients (n, %)
Anticoagulation therapy		
VKA		
Thrombin inhibitors		
Rivaroxaban		
Apixaban		
ASA		
Other anticoagulants		
None		
Antiarrhythmic drugs		
Class I		
Class II		
Class III		
Class IV		
Digitalis		
Other		
Other medications		
ACE-inhibitors		
ATII-antagonists		
Beta-blocker		
Calcium-antagonists		
Diuretics		
Nitrates		
Statines		
Antidiabetic medications		
Thyroid medications		

Table 23 – Demographic characteristics after matching

Age groups	Rivaroxaban cohort (n, %)			VKA cohort (n, %)		
	Female	Male	Total	Female	Male	Total
0-19						
20-29						
30-39						
40-49						
50-59						
60-64						
65-74						
≥75						
Total						

Table 24 – Demographic characteristics - statistics after matching

Age	Mean	Standard deviation	Minimum	Median	Maximum
Rivaroxaban cohort					
Female					
Male					
Total					
VKA cohort					
Female					
Male					
Total					

Table 25 – Type of AF diagnosis after matching

ICD-10-GM code	Type of AF	Rivaroxaban cohort (n, %)	VKA cohort (n, %)
I48.0	Paroxysmal		
I48.1	Persistent		
I48.2	Permanent		
I48.3	Typical		
I48.4	Atypical		
I48.9	Unknown		
Total			

Table 26 – CHADS₂ risk score after matching

CHADS₂ risk score value	Rivaroxaban cohort (n, %)	VKA cohort (n, %)
0		
1		
2		
3		
4		
5		
6		

Table 27 – CHA₂DS₂-VASc risk score after matching

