CHA₂DS₂-VASc risk score value	Rivaroxaban cohort (n, %)	VKA cohort (n, %)
0		
1		
2		
3		
4		
5		
6		
7		
8		
9		

Table 28 – Comorbidities after matching

Comorbidity	Rivaroxaban cohort (n, %)	VKA cohort (n, %)
Hemorrhagic diathesis due to anticoagulants and antibodies		
Coagulopathy, not specified		
Hyperthyroidism		
Diabetes mellitus		
Hyperlipidemia		
Cerebral transitory ischemia and related problems		
Essential hypertension		
Angina pectoris		
Myocardial infarction		
Other acute ischemic heart disease		
Chronic ischemic heart disease		
Pulmonary embolisms		

Heart failure Intracerebral hemorrhage Other non-traumatic intracranial bleeding Cerebral infarction Stroke, not referred to as bleeding or infarction Hemorrhage or intracranial bleeding or cerebral infarction or stroke Peripheral vascular disease, not specified Deep thrombosis on leg and pelvic veins Functional dyspepsia Hepatic insufficiency Renal insufficiency Chronic renal disease, stage 1 Chronic renal disease, stage 2 Chronic renal disease, stage 3 Chronic renal disease, stage 4 Chronic renal disease, stage 5 Cancer	
---	--

Table 29 – Co-medications after matching

	Rivaroxaban cohort (n, %)	VKA cohort (n, %)
Anticoagulation therapy		
VKA		
Thrombin inhibitors		
Rivaroxaban		
Apixaban		
ASA		
Other anticoagulants		
None		
Antiarrhythmic drugs		
Class I		
Class II		
Class III		
Class IV		
Digitalis		
Other		
Other medications		

ACE-inhibitors
 ATII-antagonists
 Beta-blocker
 Calcium-antagonists
 Diuretics
 Nitrates
 Statines
 Antidiabetic medications
 Thyroid medications

Table 30 – Standardized Differences before and after matching

Demographic and characteristics	Standardized differences before matching	Standardized differences before matching
Age		
Gender		
Type of atrial fibrillation		
I48.0		
I48.1		
I48.2		
I48.3		
I48.4		
I48.9		
Stroke risk score CHA2DS2 VASc		
1		
...		
9		
No of Comorbidities		
1		
... >10		
Separate Comorbidites		
Cancer		
...		

Table 31 – Primary endpoints after matching

Description	Rivaroxaban cohort (n, %)	VKA cohort (n, %)	HR (HR, CI)
Ischemic stroke			
Intracranial hemorrhage (ICH)			

Table 32 – Composite cerebral benefit endpoint after matching

Description	Rivaroxaban cohort (n, %)	VKA cohort (n, %)	HR (HR, CI)
Composite cerebral			

benefit (Ischemic stroke and Intracranial hemorrhage (ICH))

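### Type of AF is coded and balance-checked but cannot enter the adjusted Cox model and is not named for the propensity score; several section 9.3.1 drug classes also lack a Table 2 row

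*Protocol*

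**What the plan says.** Section 9.7.1.2 plans two adjusted analyses and gives each its own source of covariates.

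- **Multivariable Cox model.** Covariates are "A subset of the variables depicted in Table 2 which were selected on an empirical basis". Table 2 is therefore the ceiling: what has no row there cannot be selected.
- **1:1 matching.** "In this study, we will estimate propensity scores from all measured factors noted above", entered "with no further variable selection". Earlier in the same section the score is described more broadly as the probability of exposure "given all that is known about a patient (i.e. patient characteristics and covariates". No list of factors follows either statement.

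Type of AF is defined by I48 code in Annex 2, Table 5. It has its own result tables before matching (Table 18) and after matching ("Table 25 – Type of AF diagnosis after matching"), and a block of rows, I48.0 to I48.9, in "Table 30 – Standardized Differences before and after matching".

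Under the label "Other cardiovascular drugs", section 9.3.1 lists antiarrhythmics, beta-blockers, ACE inhibitors, ARBs, calcium-channel blockers, diuretics, antiplatelets and NSAIDs. It also refers to Table 13 for co-medications.

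Section 9.7 states that no separate SAP will be written, so by the protocol's own account these statements are the full specification.

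**The concern.** By giving type of AF standardized-difference rows, the plan treats it as a variable on which the two cohorts should be comparable. Yet it appears neither among the baseline characteristics nor in Table 2. If type of AF influences both the choice of anticoagulant and the risk of stroke, the multivariable hazard ratio cannot be adjusted for it. Whether the matched hazard ratio accounts for it depends on how the programmer reads an unlisted factor set. Two programmers could build different scores and so different matched cohorts. Table 30 could then report an imbalance for which section 9.7.1.2 plans no further step, and the Cox model could not correct it.

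The drug classes raise a smaller version of the same problem. They are collected at baseline, but the multivariable model cannot use most of them class by class.

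**Working it through.** No figure in the protocol is at issue. The check is a comparison of lists, followed by an illustration of size.

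**1. Type of AF**

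- Table 5: coded as I48.0, I48.1, I48.2, I48.3, I48.4, I48.9.
- Tables 18, 25 and 30: reported before and after matching and checked for balance.
- Section 9.3.1: no entry.
- Table 2: no row.
- Elsewhere before section 9.7: the subtype codes I48.0, I48.1, I48.2 and I48.9 appear only as an inclusion criterion in section 9.2.2.

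It follows that type of AF is outside the Cox pool. For the score it is not among the listed baseline factors, but the wording is open enough that it is not ruled out.

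**2. Drug classes in section 9.3.1 against Table 2**

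- Own row in Table 2: antiplatelets (B01AC) and NSAIDs (M01A). Table 2 also has rows for acetylsalicylic acid, proton-pump inhibitors and the number of unique medications.
- No own row: antiarrhythmics, beta-blockers, ACE inhibitors, ARBs, calcium-channel blockers, diuretics.
- Partial route: the Table 2 row on interacting co-medications pools the substances of Table 12 over the 90 days before index. For phenprocoumon, Table 12 lists diuretics, digitalis glycosides, amiodarone, quinidine, propafenone and metformin. Beta-blockers, ACE inhibitors and ARBs are listed for neither treatment. The only calcium-channel blocker listed under its own code is the verapamil–quinidine combination.

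Because section 9.3.1 precedes section 9.7.1.2, all these classes are among the factors the score may use. The gap concerns the multivariable Cox model alone.

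**3. Illustrative size for type of AF**

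All inputs are assumed; none is in the protocol. Treat type of AF as binary (non-paroxysmal or not), with prevalence p0 = 0.60 on phenprocoumon and p1 on rivaroxaban, and hazard ratio g for stroke. Left unadjusted, it multiplies the estimated hazard ratio by

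(1 + p1(g − 1)) / (1 + p0(g − 1)).

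| Imbalance (p1) | g = 1.2 | g = 1.3 | g = 1.5 |
|---|---|---|---|
| 5 points (0.55) | 0.991 | 0.987 | 0.981 |
| 10 points (0.50) | 0.982 | 0.975 | 0.962 |
| 15 points (0.45) | 0.973 | 0.962 | 0.942 |
| 20 points (0.40) | 0.964 | 0.949 | 0.923 |

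Example: g = 1.5 and p1 = 0.40 give (1 + 0.40 × 0.5) / (1 + 0.60 × 0.5) = 1.20 / 1.30 = 0.923.

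The baseline prevalence matters little. With p0 = 0.50, p1 = 0.40 and g = 1.5, the factor is 1.20 / 1.25 = 0.96, against 0.962 above. If rivaroxaban patients had more non-paroxysmal AF instead, the factor would exceed 1.

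The formula treats type of AF as independent of age, heart failure, CHA2DS2-VASc and the other adjusted covariates. It therefore gives crude bias, not the bias remaining after adjustment.

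**The case against.** The strongest reply concerns the propensity score. Its wording is broad, it forbids dropping factors, and section 9.7.1.2 goes on to expect balance on everything measured, with standardized differences as the check. Since Table 30 lists type of AF, the authors may well have meant it to be in the score. This stands. A reader might infer that type of AF is left out of both analyses and that the matched hazard ratio must carry its confounding. The text does not support that. It supports an unlisted factor set in which type of AF is unnamed.

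The second reply is that Table 2 is not empty of cardiovascular drugs. This also stands. A reader might infer that the Cox pool omits all of them. In fact antiplatelets, acetylsalicylic acid and NSAIDs have rows, and the interaction flag brings in some others. Table 2 also holds several main indications for the missing classes: hypertension, heart failure, coronary disease, myocardial infarction and diabetes. The protocol does not show how much drug class would add beyond these. What remains is that a pooled 90-day flag is not class-level adjustment, and that some classes are absent from it.

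The third reply is that the size is entirely assumed. That is correct. A reader might set these factors beside the ROCKET-AF stroke hazard ratio of 0.94 in section 9.5 and conclude that the bias could equal that whole effect. Of the twelve values in the grid, only 0.923 is below 0.94, and 0.942 merely rounds to it. That comparison should not be used as evidence of the bias to expect.

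**Conclusion.** The point holds in a limited form. It is firm that type of AF, which the study already derives and checks for balance, is outside the adjusted Cox model. It is also firm that six drug classes in section 9.3.1 have no Table 2 row of their own, which affects the multivariable Cox model only. For the propensity score, the defect is that type of AF is not named in an unlisted set; its exclusion is not established.

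Neither the size nor the direction of any confounding can be derived from the protocol. The range of about 0.99 to 0.92 rests on an assumed 60% prevalence, an imbalance of 5 to 20 points with less non-paroxysmal AF on rivaroxaban, and a confounder hazard ratio of 1.2 to 1.5. It also takes no credit for correlated covariates already in the model. No magnitude was worked out for the drug classes. The case for change is that the correction is nearly free, not that a material bias has been shown.

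**What to change.** - Add type of AF to section 9.3.1 and Table 2 with a single definition that works when outpatient diagnoses are dated only by quarter. One option is the most advanced specific I48 subtype recorded in the baseline period or index quarter, with I48.9 alone as unspecified. State how I48.3 and I48.4 are handled, since both appear in Tables 5 and 30 but not among the qualifying codes in section 9.2.2.
- Name type of AF explicitly among the propensity-score factors, and include it in the adjusted Cox models.
- Add antiarrhythmics, beta-blockers, ACE inhibitors, ARBs, calcium-channel blockers and diuretics to Table 2 as separate rows, so that the multivariable Cox model can use them.

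The cost is a few rows and model terms. The planned output tables already require type of AF (Tables 18 and 25) and the co-medications (Tables 22 and 29). With about 17,000 and 30,000 patients expected, the loss of precision should be negligible. The unspecified I48.9 group stays a mixed category, so adjustment for type of AF will be incomplete.

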9.2.2 Selection criteria

The study population will consist of all patients, newly initiated on Rivaroxaban or Phenprocoumon with an NVAF diagnosis meeting the following inclusion and exclusion criteria

Inclusion criteria:

- First dispense date of Rivaroxaban (15mg or 20mg - PZN based) or Phenprocoumon (PZN based) between January 1, 2012 and December 31, 2015
- At least two verified outpatient diagnoses or one inpatient diagnosis (main or secondary diagnosis) of NVAF (ICD-10 GM I48.0/ I48.1/I48.2/I48.9) in the individual time frame of 4 quarters before the index date (pre-index period) or within the index quarter
- Patients will be required to have 4 quarters of enrollment for the assessment of baseline characteristics and be observable and insured in the database for at least one day after their individual index date (post-index period)
- ≥ 18 years of age

Exclusion criteria:

- Patients with valvular AF [4 quarters prior to the index date] (see Table 5)
- Pregnancy [4 quarters prior to index date]

- Malignant cancers [4 quarters prior to the index date or “condition after”] (see Table 10)
- Transient cause of AF [4 quarters prior to index date] (see Table 5)
- Patients with VTE (pulmonary embolism or DVT) [60 days before index] (see Table 10)
- Patients with major surgery defined as hip or knee replacement [60 days before index] (see Table 10)
- Prescriptions of OACs (Rivaroxaban, VKA, Dabigatran, Apixaban) before index date [4 quarters prior to index date] (see Table 3, Table 4)
- Patients receiving more than one anticoagulant substance (Apixaban, Dabigatran, Rivaroxaban or Phenprocoumon) or more than one dosage of a substance on the index date (see Table 3, Table 4)
- *For sensitivity analysis* ([see data analysis section](#)) : Patient with any of the events defined in the combined endpoints [4 quarters prior to index date or “condition after”] (see Table 6)
- Patients with dialysis [4 quarters prior to index date] (see Table 10)

[figure not shown]

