9.3.2 Exposure

There are two exposures: New use of Rivaroxaban and new use of Phenprocoumon. Exposure will be defined as one or more prescriptions for the target drug (Phenprocoumon or Rivaroxaban). These prescriptions will be identified using the anatomical therapeutic chemical (ATC) and Pharmazentralnummer (PZN) drug codes including dose and package size (listed in the Annex 2, Table 3 and Table 4).

The exposure start date (index date in the index quarter) for each patient will be defined as the dispense date of the first Rivaroxaban or Phenprocoumon prescription.

Exposure time

Time from index date: Days of supply + Days of potential hospitalizations + Gap period (if no prescription immediately follows). Hospitalizations related to outcome measures will be considered as outcome event.

Gap period

A gap period is allowed when treatment is discontinued before censoring the patient for discontinuation. Patients will be considered as being exposed until 30 days after the end of supply.

Days of supply

Since Rivaroxaban is prescribed with a fixed dose, the number of days of supply corresponds to the size of the package, or the number of days until new prescription, if smaller. Assessing the number of days of supply for Phenprocoumon will be different.

Phenprocoumon Days of Supply:

To account for the intra- and interpersonal variability of the Phenprocoumon treatment regime (INR control and potential titration of Phenprocoumon) an empirical DDD (eDDD) based on the observed Phenprocoumon prescription patterns in the HRI database will be calculated.

The Phenprocoumon PZN code will be used to compute the Amount of Active Ingredient (AAI) dispensed to each patient of the Phenprocoumon group for each prescription. A personalized prescribed daily dose (pDDD) representing the daily dose taken during follow-up will be computed for each patient i :

$$pDDD_i = \frac{\sum_{k=1}^{K-1} AAI_{i,k}}{T_i}$$

k : index of the Phenprocoumon prescriptions during follow-up ($k \in \{1, K\}$)

T: number of days between the first and the last prescription during follow-up

The eDDD corresponds to the median of the distribution of the pPDD estimated over all patients who were solely treated with Phenprocoumon during the study period. The Exposure Time (ET) corrected from the intra- and interpersonal variability of Phenprocoumon treatments can be computed for each patient i as:

$$ET_i = \frac{\sum_{k=1}^K AAI_{i,k}}{eDDD}$$

Date of switch

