Patients who receive a prescription for an OAC other than the index OAC prescription (including other NOACs) during the follow-up period will be considered as switchers if the new prescription occurred either before the end of supply of the current prescription or within the gap period after the end of supply. The dispense date of the new OAC will be defined as the date of switch and patients will be censored.

Date of discontinuation

Discontinuation will be defined as no follow-up prescription for either Rivaroxaban or Phenprocoumon at the end of the gap period after the end of supply. Patients receiving prescriptions for Rivaroxaban 10 mg will also be considered to have terminated the treatment. The last day of the exposure time will be defined as the date of discontinuation and patients will be censored.

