We will perform 1:1 nearest-neighbor matching. After matching, we expect to see balance between the Rivaroxaban and VKA groups with respect to all measured factors. To ensure this, we will examine propensity score balance diagnostics including: (1) pre- and post-matching propensity score overlap plots; (2) pre- and post-matching c-statistics and (3) pre- and post-standardized mean differences (SMD) between the two treatment groups.

Patient time under risk and censoring

Patients will be censored in the follow-up period as follows:

Patients will be followed from index date to date of discontinuation of treatment, switch of treatment, death, end of continuous enrollment in the sick fund or end of study period without experiences any event, whichever occurs first.

Sensitivity Analyses

For this study sensitivity analyses are planned according to dosing regimen and patients with prior events of any of the events defined in the combined endpoints.

One separate analysis will be conducted for patients receiving 20mg Rivaroxaban only (standard-dose analysis). Patients will be censored once a different dose was prescribed compared to the index dose of 20mg. For patients receiving initiating 15mg Rivaroxaban baseline characteristics will be outlined descriptively.

Additionally, a separate analysis will be planned where patients with any of the events defined in the combined endpoints within the baseline period 4 quarters prior to index date or “condition after”) will be included in the analyses.

Therefore, sensitivity analyses will result in four separate cohort and patient time datasets for which a propensity score matching and a multivariate analysis will be performed.

Handling of Missing Data

Missing data will not be imputed.

Statistical Software

All analyses will be performed with SAS 9.2.

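### The 20 mg sensitivity analysis censors dose changes in the rivaroxaban arm only, and no check is planned for whether that censoring is informative

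*Protocol*

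**What the plan says.** Patients enter the main rivaroxaban cohort on either strength. The first inclusion criterion in Protocol Section 9.2.2 reads "First dispense date of Rivaroxaban (15mg or 20mg - PZN based) or Phenprocoumon (PZN based".

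The sensitivity analyses in Section 9.7.1.2 contain a dose-restricted comparison in which only one strength is kept, and its follow-up rule is this: "Patients will be censored once a different dose was prescribed compared to the index dose of 20mg". Those who start on the lower strength have no outcome comparison of their own; the section plans only a baseline description of them.

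Section 9.3.2 gives the rules that end follow-up in both arms. A switch concerns "Patients who receive a prescription for an OAC other than the index OAC prescription (including other NOACs) during the follow-up period". On discontinuation it says: "Discontinuation will be defined as no follow-up prescription for either Rivaroxaban or Phenprocoumon at the end of the gap period after the end of supply". A rivaroxaban 10 mg prescription also counts as the end of treatment. A change between 15 mg and 20 mg does not.

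Phenprocoumon dosing is treated as variable. Section 9.3.2 introduces an empirical daily dose "To account for the intra- and interpersonal variability of the Phenprocoumon treatment regime (INR control and potential titration of Phenprocoumon"), and one population median then converts dispensed quantity into exposure time.

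Section 9.7 states that no separate statistical analysis plan will be written, so these sentences are the whole specification of the dosing analysis.

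**The concern.** The 20 mg analysis adds a reason for censoring that only rivaroxaban patients can meet. A dose change happens after the index date and may follow a change in the patient's condition. Section 9.3.1 makes a link to risk plausible when it lists "CKD, which is important as risk of adverse events among patients receiving NOACs tends to differ according to renal function" among the baseline characteristics. If changers are at higher risk, their later person-time leaves the rivaroxaban arm, while phenprocoumon patients whose condition worsens in the same way stay under observation.

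The propensity score uses baseline covariates, so it cannot balance what happens afterwards. No censoring weights, uncensored version or count of dose changers is planned, and the limitations in Section 9.9 do not mention the issue. A 20 mg result that looks better than the pooled one could then be read as a dose finding when part of it comes from the censoring rule.

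**Working it through.** **1. The rules side by side**

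| Event after index | Pooled main analysis | 20 mg analysis, rivaroxaban | 20 mg analysis, phenprocoumon |
|---|---|---|---|
| No refill by end of gap | ends follow-up | ends follow-up | ends follow-up |
| Different anticoagulant | ends follow-up | ends follow-up | ends follow-up |
| Rivaroxaban 10 mg | ends follow-up | ends follow-up | not applicable |
| Change from 20 mg to 15 mg | continues | **ends follow-up** | not applicable |
| Change of phenprocoumon dose | continues | not applicable | **continues** |

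The 20 mg to 15 mg row rests on reading the switch rule as a change of substance. That reading fits the text: if the general rule already covered strengths, the extra sentence for the 20 mg analysis would not be needed.

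**2. Possible size of the effect**

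The protocol has no figure for this, so both inputs are assumed. Let q be the share of the 20 mg starters' person-time that falls after a dose change, and k the event rate in that time relative to the retained time (rate L). The comparison target is 20 mg starters followed through the change. Rates are taken as constant, so that the rate ratio stands for the hazard ratio.

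- Full rivaroxaban rate: L × [(1 − q) + qk]
- Rivaroxaban rate after censoring: L
- With a true hazard ratio of 1, the phenprocoumon rate equals the full rivaroxaban rate, so observed HR = 1 / [1 + q(k − 1)]

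| q | k = 0.5 | k = 1 | k = 1.5 | k = 2 |
|---|---|---|---|---|
| 5% | 1/0.975 = 1.03 | 1.00 | 1/1.025 = 0.98 | 1/1.05 = 0.95 |
| 10% | 1/0.95 = 1.05 | 1.00 | 1/1.05 = 0.95 | 1/1.10 = 0.91 |
| 20% | 1/0.90 = 1.11 | 1.00 | 1/1.10 = 0.91 | 1/1.20 = 0.83 |

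For scale, two of the stroke hazard ratios in the Section 9.5 power table are 0.94 and 0.86.

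**3. What a 15 mg comparison could show**

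The Section 9.5 power table concerns the pooled cohort. Its rates, read as one-year proportions with 17,000 and 30,000 patients and a two-sided 5% level (assumed), give power of 0.113, 0.955, 0.761 and 0.999 for the four rows that list rates. The stated values are 0.1105, 0.9581, 0.7601 and 1.000. One person-year per patient is therefore in keeping with the protocol's own planning.

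Assume that 20% to 40% of the 17,000 rivaroxaban patients start on 15 mg (3,400 to 6,800 matched pairs). The 95% CI factor is exp(1.96 × 2/√events).

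- Stroke, low end (REVISIT-US rates): 3,400 × (0.0054 + 0.0083) ≈ 47 events, factor 1.78
- Stroke, high end (0.0134 in both arms): 6,800 × 2 × 0.0134 ≈ 182 events, factor 1.34
- ICH, low end (Rocket-AF rates): 3,400 × (0.005 + 0.007) ≈ 41 events, factor 1.85

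**The case against.** The strongest reply is that the rule matches the stated question. An analysis of patients on 20 mg only should stop counting when they leave 20 mg, and the whole study is on-treatment. Phenprocoumon is titrated and its daily dose is not observed, so no mirror rule exists. The asymmetry comes from comparing a fixed-dose drug with a titrated one and is not in itself an error. Renal stages are listed covariates and the score is re-estimated in each dataset, so dose changes predicted by baseline renal disease are partly covered. All of this stands. It does not cover risk that changes after the index date, and the lack of a mirror rule is why an uncensored run is the natural check.

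A reader might infer that the 20 mg hazard ratio is biased in favour of rivaroxaban. The documents do not support that. They do not say how often strengths change, why, or at what risk. The renal remark is about adverse-event risk and baseline description, not about dose changes. There is no bias at k = 1, and the direction reverses below 1.

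A reader might also infer that the dosing analysis cannot test the pooled result. That goes too far: a re-matched 20 mg estimate set beside the pooled one tests part of its robustness. It says nothing about 15 mg starters, who stay in the pooled estimate. The protocol promises no 15 mg outcome comparison, though, and the database holds no laboratory values, so describing those patients only at baseline is defensible.

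**Conclusion.** The point holds as a conditional weakness of one sensitivity analysis. Dose-change censoring applies to rivaroxaban alone, may be informative, is not corrected by baseline matching and has no planned check. If 10% of person-time follows a dose change and carries 1.5 to 2 times the earlier rate, a null effect would appear as 0.95 to 0.91. At equal risk nothing happens, and at half the rate it would appear as 1.05. These figures rest on assumed inputs that the sponsor can replace from the data. The primary pooled hazard ratios are untouched, because there a change between 15 mg and 20 mg does not end follow-up. The lack of a 15 mg estimate limits what can be said about consistency across doses but is not an error.

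**What to change.** In Section 9.7.1.2, keep the planned version censored at dose change and add beside it:

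- the cohort defined by a 20 mg index dispensing, followed through later 15/20 mg dispensings under the same discontinuation and switch rules as phenprocoumon;
- the number of patients censored for dose change;
- a sentence in the report that dose-change censoring applies to one arm only.

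Optionally, add a re-matched comparison of 15 mg starters with phenprocoumon, labelled descriptive, noting residual confounding by renal function and the low precision shown above.

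This takes one extra model run, two with the optional comparison, on existing data and code, plus a paragraph of text. The price is two 20 mg estimates to explain and, if the option is taken, a wide 15 mg interval.
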